14 SECONDARY OUTCOME MEASURES

ANALYSES:

Additional analyses of safety will summarize the magnitude of CD4+ T-cell changes baseline to post-treatment time points (means over time, participant-specific curves). Analyses will also summarize the number of **participants** who exhibit on two consecutive measurements HIV RNA >200 copies/mL on conventional assay. Tolerability will be assessed by the number of **participants** who prematurely discontinue study treatment and the reasons for discontinuation. **The analysis population for these CD4, HIV-RNA, and tolerability assessments will be the safety population.**

Analyses of secondary virologic and immunologic outcomes will parallel the primary analysis. **The secondary efficacy analysis population is defined as participants who completed at least 6 weeks of sirolimus.** Paired t-tests will compare measurements pre-treatment (averaged) to the measurement at treatment week 20 for the primary efficacy population and treatment week 4 for the secondary efficacy population. Graphical approaches will summarize the virologic and immunologic measurements over time, **through treatment week 32 for the primary efficacy population and, separately, through treatment week 4 for the secondary efficacy population.** Soluble markers (eg, IL-6 levels) will be log10-transformed.

Analyses will also summarize changes in immunologic and virologic measures after discontinuation of study treatment. **Paired t-tests will compare the measurements at treatment week 20 to treatment week 32* for the primary efficacy analysis population.**

For the primary analysis population, trough sirolimus levels (during the 20 weeks of treatment) will be summarized by descriptive statistics on the participant-specific average of all available sirolimus levels (minimum, 10th, 25th, median, 75th, 90th, maximum). In addition, the number of trough levels per participant will be summarized. To provide information regarding pharmacodynamics, scatterplots and correlations

will assess the relationship between average trough level and change from baseline to week 20 outcomes. These correlations will be restricted to outcomes with evidence of change following sirolimus treatment.

Associations between changes in the various immunologic and virologic measurements will be evaluated using scatterplots and correlations coefficients.

OUTCOMES:

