9.4 Sample Size and Accrual

Regarding the assessment of safety/toxicity (see section 9.2.1.1), the sample size of 30 sirolimus-treated **participants** will provide >90% probability of observing a sirolimus-related adverse event that would occur in 8% or more of treated **participants**.

The primary efficacy analyses will evaluate paired baseline and post-sirolimus therapy immunologic and virologic measurements to detect changes; these measures are assumed stable on long-term suppressive ART (see section 2.2.6). Allowing 17% sample size adjustment for lost to follow-up and treatment discontinuation for the planned as-treated analyses (i.e., n=25 **participants** assumed evaluable), the study will have 80% power to detect a 0.59 standard deviation (SD) effect size based on a two-sided, alpha=0.05, 1-arm t-test. This effect size translates (under assumed normality) into a probability of 0.72 that a **participant** receiving sirolimus will have an observed increase in HIV-specific CD8 immunity (see section 9.2.1.2). Similarly, power would be 80% to detect a corresponding decrease in cell-associated RNA (see section 9.2.1.3). The null hypothesis is that the probability is 0.5 (equally likely to observe increase or decrease). For residual viremia (SCA, see section 9.2.1.3), effect size is slightly larger due to anticipated left-censoring below assay limits. From numerical simulation based on a 1-arm t-test (imputing half the lower limit for SCA results below assay limits), power is estimated to be 80% to detect an underlying effect size of 0.67 SD; this 80% power corresponds to assuming that the probability is 0.5 (50%) for a baseline (pre-entry, entry) SCA to be below assay limit compared to 0.75 (75%) after treatment. The assumption that 50% of SCA results will be below assay limits at baseline is supported by findings from ACTG A5276s in which 56% of 668 SCA measurements after 192 and 208 weeks of suppressive ART on 334 **participants** were below assay limits (<1 copy/mL). Analyses will also jointly evaluate efficacy measurements at the multiple post-treatment time points (e.g., the change from baseline to the average of the weeks 16, 24, and 32 measurements [4, 12, 20 weeks on sirolimus]), which could increase statistical power.

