9.6.1 Primary Analyses

For the primary safety analysis, \geq Grade 3 AEs attributed to study treatment and confirmed CD4+ declines (see section 9.2.1.1) will be summarized. In addition, all other reported AEs \leq Grade 2 attributed to study treatment as well as all reported events \geq Grade 2 (regardless of treatment relatedness) will be summarized. All **participants** who have been exposed to study treatment will be included in the analysis.

For the primary immunologic (see section 9.2.1.2) and virologic (see section 9.2.1.3) efficacy outcomes, post-treatment changes will be evaluated comparing measurements pre-treatment (averaged) to the measurement 20 weeks after starting study treatment, testing the null hypothesis of no difference pre-treatment versus post-treatment using a paired t-test. Log-transformations may be applied for the virologic outcomes. To address anticipated left-censoring of SCA measurements, a value one half the lower assay limit will be imputed. If feasible with the modest sample size, censored-data longitudinal data methods that statistically address the

issue of left-censoring (SCA measurements below assay limits) will also be used to evaluate and estimate treatment effects [59]. Mean and quartile plots will summarize the immunologic and virologic measurements at each visit. Because the aim of this pilot study is to investigate the biologic effects of sirolimus, the analyses will be as-treated, limited to **participants** who have data at baseline and week 32 (20 weeks on sirolimus) and who remained on study treatment and ART (and without virologic failure) through week 32. A supplemental analysis will be based on changes from baseline to the last available time point for a **participant** while on study treatment and ART (and without virologic failure).

If there is evidence that there is a significant difference between the week 0 and week 12 levels of the primary immunologic and virologic efficacy measurements, based on paired t-tests between these two time points, then the primary analysis will instead be based on a comparison of slopes pre- versus post-treatment (see 9.6.2). Both sets of results, from the paired t-test analyses and the comparison of slopes analyses, will be reported in the presentation of the study findings.

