5.3 Visit Schedule and Definition of Week for Analysis Purposes

The visit schedule for key study outcomes is shown in Table 1.

The protocol requires evaluations to be scheduled at the **treatment week 0** visit, ± 1 day at the **treatment week 1, 2 and 4** visits, ± 1 week at the **treatment week 8, 12 and 20** visits, and ± 2 weeks at the **treatment week 32*** visit. The analysis window for post-entry visits will be calculated based on the number of **weeks** since the initial dose of sirolimus and broader windows will be used (as compared to the protocol specified window) in order to minimize the impact of deviations from the desired schedule. If there are multiple evaluations within the window for a given visit, then the evaluation closest to the scheduled study week will be used (and the later measurement will be used if there are two measurements which are equally distant from the scheduled week). Table 1 **below** details the **analysis windows for clinical data**.

For the primary and secondary outcome measures, and the exploratory soluble marker outcome, a database review was conducted by the study chair to identify the time points to be tested based on the availability of samples and the duration of sirolimus use. This resulted in a total of 159 time points for 29 study participants.

- For 16 participants with the full 20 weeks of sirolimus use who will constitute the primary efficacy population: treatment weeks -12, 0, 4, 12, 20 and 32*
- For the 13 participants with at least 6 but less than 20 weeks of sirolimus use: treatment weeks -12, 0, 4, 12 and 20*

Note: One participant went off study early and only has weeks -12, 0 and 4.

Note: Treatment weeks 32* and 20* refer to time points after sirolimus discontinuation. Data from these time points will be used to assess durability of treatment effects and will not be included in the as-treated analysis of efficacy.

Table 1: Study Visit Schedule and Analysis Windows

Evaluation	Screening	Entry	Sirolimus Initiation	Post-Entry Evaluations						
	Treatment Week	-12	0	1	2	4	8	12	20	32
Analysis Window (Weeks Post-Sirolimus Initiation)		0	(0 – 1]	(1 – 3]	(3 – 6]	(6 – 10]	(10 – 16]	(16 – 26]	(26 – 37]	
Clinical Assessment	X	X	X	X	X	X	X	X	X	X
Hematology	X	X	X	X	X	X	X	X	X	X
Liver Function Tests	X	X	X	X	X	X	X	X	X	X
Blood Chemistry	X	X	X	X	X	X	X	X	X	X
Calculated Creatinine Clearance	X	X	X	X	X	X	X	X	X	X
Urinalysis	X		X			X	X	X		
CD4+/CD8+	X	X	X		X	X	X	X	X	X
Plasma HIV-1 RNA	X	X	X			X	X	X	X	X

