13.2 Primary Efficacy Analyses

Because the aim of this pilot study is to investigate the biologic effects of sirolimus, the primary efficacy analysis population is defined as participants who completed the full 20 weeks of sirolimus treatment, and who remained on sirolimus and ART without virologic failure. For each primary efficacy outcome, analysis will be limited to participants who have data both at baseline and after 20 weeks of sirolimus. Based on the specimens mobilized for testing, 16 participants are anticipated to meet these criteria and be included in the primary efficacy analysis.

Tables summarizing completeness (N), mean, standard deviation, median, 25th and 75th percentiles and min/max of HIV-1 Gag-specific CD8+ T-cells by intracellular staining for IFN-gamma, CD4+ T-cell associated HIV-1 RNA, and plasma HIV-1 RNA by SCA at baseline and at **treatment week 20**.

For the primary immunologic and virologic efficacy outcomes, post-treatment changes will be evaluated comparing measurements pre-treatment (averaged) to the measurement 20 weeks after starting study treatment, testing the null hypothesis of no difference pre-treatment versus post-treatment using a paired t-test.

Log10-transformations will be applied for the virologic outcomes.

Cell-associated HIV-1 RNA (CA-RNA) was measured in terms of copies/ 10^6 PBMCs. These results were normalized to copies/ 10^6 CD4+ T-cells by dividing by (CD4% / 100).

To address anticipated left-censoring of SCA and CA-RNA measurements, a value one half the lower assay limit will be imputed and analyzed for results below assay limit. If feasible with the modest sample size, censored-data longitudinal data methods that statistically address the issue of left-censoring (SCA measurements below assay limits) will also be used to evaluate and estimate treatment effects [Vaida and Liu 2009]. Plots will summarize the

immunologic and virologic measurements at each visit (means over time, participant-specific curves).

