14.1 CD4+ T-cell counts

14.2 HIV-1 RNA levels by conventional assay

14.3 HIV-1-specific CD4+ cell responses and HIV-1-specific CD8+ cell responses (other than IFN-gamma)

Measured by:

- **IFN-gamma**
- **CD107a**
- **CD40L**
- **IL-2**
- **MIP1B**
- **TNF-alpha**

14.4 T-cell activation, proliferation and subsets: % CD4+ and CD8+ cells CCR5+, CD27+, CD69+, Ki67+, PD1+, Naïve (CD45RA+CCR7+), Central Memory (CD45RA-CCR7+), Effector Memory (CD45RA-CCR7-) and Terminally Differentiated (CD45RA+CCR7-)

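### The SAP omits, with no recorded reason, the protocol's supplemental last-on-treatment efficacy analysis, while 13 of 29 tested participants fall outside the week 20 contrast

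*SAP*

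**What the plan says.** **Protocol.** Section 9.6.1 limits the primary efficacy analysis to participants with baseline and study week 32 data who stayed on sirolimus and ART, without virologic failure, to that point. It then adds: "A supplemental analysis will be based on changes from baseline to the last available time point", under the same on-treatment conditions. The wording is firm; it is not qualified by feasibility or discretion.

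**SAP, primary analysis.** Section 13.2 keeps the completer population and the paired t-test, and says that "16 participants are anticipated to meet these criteria and be included in the primary efficacy analysis". Its only supplements are censored-data methods, if feasible, and a slope comparison that runs only when two significance conditions are met.

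**SAP, wider population.** Section 14 defines a secondary efficacy population with at least 6 weeks of sirolimus. The paired tests compare baseline "to the measurement at treatment week 20 for the primary efficacy population and treatment week 4 for the secondary efficacy population". The plots for the wider population also stop at treatment week 4.

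**SAP, samples.** Section 5.3 lists 159 time points in 29 participants. "For the 13 participants with at least 6 but less than 20 weeks of sirolimus use", the samples are treatment weeks -12, 0, 4, 12 and 20*, with one exception: "One participant went off study early and only has weeks -12, 0 and 4". The starred time points, taken after sirolimus was stopped, "will not be included in the as-treated analysis of efficacy". Week 12 carries no star.

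**SAP, version history.** Section 2 logs the work on the two efficacy populations (version 3.0) and the changed handling of baseline differences (version 4.0). It does not mention the supplemental analysis.

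**The concern.** The completer comparison uses people selected by what happened after treatment began. The protocol accepted this because the aim is biological effect, and it paired the comparison with an analysis that carries early stoppers at their last on-drug value. If the SAP is followed as written, the companion analysis will not be produced.

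The omission weighs more now than when the protocol was written. The sample size section allowed for modest attrition ("Allowing 17% sample size adjustment for lost to follow-up and treatment discontinuation for the planned as-treated analyses"); the SAP anticipates that little more than half of those tested will enter the week 20 contrast. A reader of the results would see a week 20 change in completers and, for the wider group, at most a week 4 change, which may not be reported for the primary outcomes at all.

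**Working it through.** **1. The plan's own figures reproduce.**
- Time points: 16 × 6 + 12 × 5 + 1 × 3 = 96 + 60 + 3 = 159, as SAP 5.3 states. Counting all 13 early stoppers at five samples would give 161, so the participant with three samples is one of the 13.
- Planned evaluable number: 30 × (1 − 0.17) = 24.9, or 25. One-sample t-test power (noncentral t, n − 1 degrees of freedom, noncentrality d√n) at n = 25, d = 0.59, two-sided 0.05 is 0.808, matching the stated 80%.

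**2. How many are outside the week 20 contrast.**
- SAP: 13/29 = 44.8% of those tested.
- Protocol: 5/30 = 16.7% of those enrolled.
- The denominators differ (tested with at least 6 weeks of drug, against enrolled), so this shows scale and is not a like-for-like ratio.

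**3. What early stoppers can contribute.**
- Their selected time points: 12 × 5 + 3 = 63, and 63/159 = 39.6%.
- On-drug values after baseline: week 4 for all 13. Week 12 exists for 12 of them, but anyone who stopped between weeks 6 and 12 was off drug by then. The SAP gives no count, so the number on drug lies between 0 and 12.

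**4. The two analyses side by side.**

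| | Protocol 9.6.1 supplement | SAP 14 wider-population test |
|---|---|---|
| Outcomes | Primary efficacy outcomes | Secondary outcomes; the primary three not named |
| Minimum exposure | None stated | 6 weeks of sirolimus |
| Time point | Last one on drug | Week 4 for everyone |
| ART and virologic failure | Both conditions stated | Not restated |
| Exposure compared | Mixed, about 4 to 20 weeks | Common, 4 weeks |

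Neither contains the other. Even if no week 12 sample was on drug, the protocol analysis would still differ, because it sets early stoppers' week 4 values alongside completers' week 20 values.

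**5. Illustration only.** Let completers change by the design effect of 0.59 SD and early stoppers by a fraction f of it (f is assumed; the documents give none). The mean over 29 is 0.59 × (16 + 13f)/29:
- f = 1: 0.59 SD
- f = 0.5: 0.59 × 22.5/29 = 0.46 SD
- f = 0: 0.59 × 16/29 = 0.33 SD

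With the SD unchanged, power is about 0.60 for the 16 completers at 0.59 SD, and about 0.87, 0.66 and 0.40 for the pooled 29 at these three means. Pooling can therefore raise or lower power.

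A direct comparison of 13 stoppers with 16 completers, with equal SDs, would have a 95% half-width of 2.052 × √(1/16 + 1/13) = 0.77 SD. The fix does not ask for that test; the figure shows only how little 29 people can resolve.

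**The case against.** The best defence is that the week 4 test was designed as the replacement. It was added after version 1.0 and is logged under version 3.0. Its logic can be inferred: the week 4 analysis window in SAP Table 1 closes at 6 weeks, so a 6-week minimum keeps everyone on drug at the tested point, which week 12 cannot guarantee. It also compares all 29 at the same nominal exposure. This has real merit, and the fix keeps the test. But the SAP nowhere says that it replaces the protocol analysis, does not name the primary outcomes for it, and leaves any on-drug week 12 values unused.

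Second, the last-on-drug analysis is not a clean check on selection. A smaller pooled mean could reflect who stopped or how briefly they were treated, and the analysis alone cannot tell which. This stands and limits what may be claimed for it.

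Third, a reader might see a contradiction in SAP 14.3, whose title includes "HIV-1-specific CD8+ cell responses (other than IFN-gamma" while its list includes IFN-gamma. The exclusion can be read as applying to CD8+ cells only, whose Gag IFN-gamma response is primary, so nothing rests on it here. What remains is that section 14 does not list cell-associated RNA or single-copy RNA. SAP 5.3 does say that the samples were selected for the primary as well as the secondary outcomes, so the measurements are planned even though the test is not stated.

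Fourth, silence does not withdraw a protocol commitment, and SAP 1 allows the team to modify the plan. True, but SAP 13.2 carries over most of the rest of 9.6.1, and SAP 1 makes this document the core of any primary report. Followed as written, it leaves the analysis out.

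**Conclusion.** The point holds as an unexplained departure of the SAP from the protocol. An analysis that the protocol says will be done is absent, no reason is recorded, and 13 of 29 tested participants (45%) lie outside the contrast that it was meant to accompany. This rests on the text and on counts that reconcile to 159. The means under assumed f and the 0.77 SD half-width are illustration only.

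Four stronger readings are tempting, and the documents do not support them:
- *Early stoppers get no efficacy analysis.* The week 4 test includes them.
- *The completer t-test is invalid.* It is the protocol's own primary analysis and stays primary.
- *The analysis was deliberately removed.* Earlier SAP versions cannot be seen, and the version history is silent on it.
- *All 12 week 12 samples were on drug because week 12 is not starred.* Sirolimus could have stopped at any time from week 6.

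Restoring the analysis should be done, but it is a coarse sensitivity analysis. It cannot by itself separate selection from duration of exposure.

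**What to change.** In SAP 13.2, add for Gag-specific CD8+ cells, cell-associated RNA and single-copy RNA:

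1. The protocol 9.6.1 supplement: a paired comparison of baseline with the last tested value on sirolimus and ART without virologic failure. For completers this is week 20. For early stoppers it is week 12 if those conditions still hold then, otherwise week 4. State how participants with virologic failure are handled.
2. A statement that the week 4 paired test also covers these three outcomes, with results shown for completers and early stoppers. This gives the equal-exposure view that the last-on-drug analysis lacks.
3. The number of early-stopper week 12 samples that were on drug, and the number of treated participants left out because no samples were selected. The protocol sets no 6-week minimum.

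Present these beside the completer t-test as sensitivity results, with no claim of added power. If the team intends the week 4 test to replace the protocol analysis, the SAP must at the least say so and give the reason; the week 12 values would then stay unused.

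The cost is about a paragraph and a little programming, with no new sample selection. The drawbacks are the mix of about 4 to 20 weeks of exposure, little added information if few week 12 samples were on drug, and the continued absence of anyone treated for under 6 weeks, if there are any.

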Sirolimus use ($p=0.04$) and longer duration of follow-up post-transplant (marginally; $p=0.06$) were associated with a decreased proviral DNA level in the multivariate model (model adjusted for baseline HIV DNA, baseline CD4+ cell count, time-varying sirolimus use, and study week); higher baseline proviral HIV DNA ($p<0.0001$) and lower CD4+ cell count ($p=0.001$) were associated with increased proviral HIV DNA level post-transplant. Sirolimus use was also significantly associated with lower proviral DNA in univariate analysis ($p=0.02$).

As compared to subjects on other immune-modulating drugs such as cyclosporine and tacrolimus, the relative difference in HIV DNA levels was approximately $0.3 \log_{10}$ copies/mL (see Figure 1). Figure 2 shows the proviral HIV DNA level over time by sirolimus exposure. No significant predictors of cell-associated RNA post-transplant were identified in the multivariate model (data not shown). These post-hoc analyses have several limitations, including the lack of consistent use of sirolimus monotherapy among the study population. As a result, the findings may have been influenced by various uncontrollable biases, and further data regarding sirolimus use and viral reservoirs from the kidney transplant population are not available. Taken together, a proof-of-concept study of sirolimus in HIV-infected individuals on suppressive ART is warranted to elucidate the safety and efficacy of mTOR inhibition on latent reservoirs and anti-HIV immune responses and inflammation.

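### The only planned exposure-response analysis of the efficacy outcomes is run only for outcomes that first pass an undefined test of mean change

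*SAP*

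**What the plan says.** SAP section 14 (Analyses) averages all available trough levels over the 20 treatment weeks for each participant in the primary analysis population. To inform pharmacodynamics, scatterplots and correlations "will assess the relationship between average trough level and change from baseline to week 20 outcomes". The next sentence sets the restriction: "These correlations will be restricted to outcomes with evidence of change following sirolimus treatment". No test, p-value, effect size or time point is attached to it.

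The nearest candidate for the test is the main efficacy comparison in SAP 13.2, which compares averaged baseline with treatment week 20, "testing the null hypothesis of no difference pre-treatment versus post-treatment using a paired t-test". On numbers, the same section says: "Based on the specimens mobilized for testing, 16 participants are anticipated to meet these criteria and be included in the primary efficacy analysis". Protocol 9.4 had planned for 25 evaluable participants.

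**The concern.** The paired test asks whether the average participant changed. The correlation asks whether participants with higher exposure changed more. Either can be true without the other. If only participants with higher troughs respond, the mean change is diluted and may not reach significance, and the rule then closes the one analysis that could show the pattern.

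Three features make this worse than a routine economy:

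- The test that would act as the gate has lost power, because 16 participants are expected where 25 were planned.
- The criterion is not written down, and the SAP introduction allows the plan to be changed in light of the study's own findings. Which outcomes qualify could therefore be settled after the results are seen.
- Without a stated criterion, a reader of the report cannot be sure whether a missing correlation means that no relation was found or that none was looked for.

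At stake is whether exposure-response results for the key outcomes are reported completely or selectively.

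**Working it through.** **Inputs.** Protocol 9.4: "the study will have 80% power to detect a 0.59 standard deviation (SD) effect size based on a two-sided, alpha=0.05, 1-arm t-test", with 25 evaluable. SAP 13.2: 16 anticipated. Assumed, because the SAP is silent: the gate is the two-sided paired t-test at p<0.05, with looser gates also shown. Also assumed: the true correlation between trough and change, for which the documents give no value.

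**Step 1: reproduce the plan's power.** A paired t-test with n participants and standardised mean change d has n−1 degrees of freedom and noncentrality d√n. For n=25 and d=0.59 the noncentrality is 0.59 × 5 = 2.95 and the critical t (24 df) is 2.064. Power is 80.8%, which agrees with the stated 80%.

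**Step 2: the same test at n=16.** Noncentrality is 0.59 × 4 = 2.36 and the critical t (15 df) is 2.131. Power is 59.8%, so the gate stays closed for 100 − 59.8 = 40.2% of true 0.59 SD effects. At n=25 it would be 19.2%.

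**Step 3: other readings of the gate (n=16, d=0.59).**

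| Gate (two-sided) | Correlation skipped |
|---|---|
| p<0.05 | 40.2% |
| p<0.10 | 27.2% |
| p<0.15 | 20.1% |
| p<0.20 | 15.6% |

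If a response confined to higher exposure dilutes the mean change to 0.3 SD (an illustrative value), the noncentrality is 1.2 and a p<0.05 gate closes in 79.7% of trials.

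**Step 4: SCA.** Protocol 9.4 treats this outcome separately: "power is estimated to be 80% to detect an underlying effect size of 0.67 SD", allowing for results below the assay limit. With censoring ignored, 0.67 SD at n=16 gives 70.7% power and a 29.3% skip rate. That understates the loss: the same formula at n=25 gives 89.5%, against the plan's 80%. The rate with censoring was not computed.

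**Step 5: effect on the correlation.** At n=16 the critical t (14 df) is 2.145, so the critical |r| is 2.145/√(14 + 2.145²) = 0.497. Trials were simulated (100,000 per row) as change = 0.59 + ρ × standardised trough + √(1−ρ²) × error, with a p<0.05 gate.

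| True ρ | Significant, no gate | Gate open | Significant given gate open | Examined and significant |
|---|---|---|---|---|
| 0.3 | 20.8% | 59.8% | 19.3% | 11.6% |
| 0.5 | 53.4% | 60.0% | 50.4% | 30.2% |

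The last column is the product of the two before it. At ρ=0.5 the mean r is 0.47 when the gate opens and 0.51 when it does not, so the gate hardly distorts the estimate. The loss is in analyses not run.

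**Step 6: precision.** By Fisher's z, the 95% CI is tanh(atanh r ± 1.96/√13). For r=0.5 it is 0.01 to 0.80. For r=0.3 it is −0.23 to 0.69.

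**The case against.** The case for leaving the rule alone has real weight.

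- **The analysis is weak in any event.** With 16 participants it needs |r| of about 0.50 to be significant. Doses are titrated towards 5–10 ng/mL (Protocol 5.1, Table 4), which narrows the exposure range by design. Troughs are not randomised: they may follow clearance, adherence or ART class, which sets the starting dose. This stands, and it limits the correlation to description. It does not justify the gate, since an interval shows imprecision and an omission hides it.
- **The gate limits false positives.** With no mean change and no relation, both tests are significant in about 0.05 × 0.05 = 0.25% of cases, against 5% for an ungated correlation. For the long list of flow and soluble-marker outcomes that is a sensible choice, and it stands.
- **No protocol objective depends on it.** The pharmacokinetic objective (Protocol 1.4.1) concerns interactions with antiretrovirals. This stands too, and it keeps the point modest.

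A reader might go further and infer that, with no control arm, this correlation is the trial's only internal evidence of a drug effect. The documents do not support that. They plan a 12-week untreated lead-in, a slope comparison before and after treatment (conditional in SAP 13.2), and a paired test of treatment week 20 against week 32 off sirolimus that is not gated (SAP 14). All bear on drift over time. They do not replace the correlation, because none uses exposure. The SAP 13.2 slope comparison also needs a significant sirolimus effect first, so it tends to close in the same cases.

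**Conclusion.** The point holds as a cheap improvement, not a major flaw. The only planned exposure-response analysis of the efficacy outcomes depends on the answer to a different question, through a criterion the SAP does not define.

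Its size is conditional. The skip rate of about 40% assumes a two-sided p<0.05 gate, 16 participants and a true 0.59 SD change; at p<0.10 to p<0.20 it is about 27% to 16%. A reader might take 40% as a property of the plan, but the SAP states no threshold. The figure does not carry over to SCA.

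The evidence lost depends on a correlation that the documents do not give. At 0.5, detection falls from about 53% to 30%; at 0.3, from about 21% to 12%. The harm is analyses lost or selectively reported, since the estimate is barely biased when the correlation is run.

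**What to change.** In SAP section 14, name four outcomes for which the scatterplot, correlation and 95% CI against average trough are reported whatever the paired test shows: Gag-specific CD8+ frequency, cell-associated RNA, SCA and cell-associated DNA. Label them exploratory. For the remaining flow and soluble-marker outcomes the restriction can stay, with its test, threshold, time point and population written down before those results are seen.

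The cost is a sentence or two and four plots. The trough averages and week 20 changes are already planned, so no visit, assay or dosing changes. The downside is four more exploratory correlations with wide intervals. Each has a 5% chance of a false positive if read as a test. If all four were null and independent, the chance of at least one would be 1 − 0.95⁴ = 18.5%. The report should therefore lead with the intervals rather than p-values.
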